## 16.5 Ethnic and Gender Distribution Chart

| TARGETED / PLANNED ENROLLMENT: Number of Subjects |              |       |       |
|---|--------------|-------|-------|
| Ethnic Category                                   | Sex / Gender |       |       |
|   | Females      | Males | Total |
| Hispanic or Latino                                | 1            | 1     | 2     |
| Not Hispanic or Latino                            | 8            | 10    | 18    |
| Ethnic Category Total of All Subjects*            | 9            | 11    | 20    |
| Racial Categories                                 |              |       |       |
| American Indian / Alaska Native                   | 0            | 0     | 0     |
| Asian   | 1            | 2     | 3     |
| Native Hawaiian or Other Pacific                  | 0            | 0     | 0     |
| Black or African American                         | 0            | 0     | 0     |
| White   | 8            | 9     | 17    |
| More Than One Race                                | 0            | 0     | 0     |
| Racial Categories: Total of All                   | 9            | 11    | 20    |

## 17.0 INVESTIGATOR OBLIGATIONS

The PI is responsible for the conduct of the clinical trial at the site and is responsible for personally overseeing the treatment of all study subjects. The PI must assure that all study site personnel, including sub-Investigators and other study staff members, adhere to the study protocol and to all applicable regulations and guidelines regarding clinical trials both during and after study completion.

All subjects are informed of the nature of the program, its possible hazards, and their right to withdraw at any time, and each subject signs a form indicating their consent to participate prior to receiving any study-related procedures (see Appendix A).

## 18.0 ADMINISTRATIVE AND REGULATORY CONSIDERATIONS

### 18.1 Pre-Study Documentation

The following documentation required by the FDA must be completed prior to initiation of the trial: FDA Form 1572; curricula vitae of the PI and all Sub-Investigators; copy of the correspondence from the IRB indicating approval of the protocol and Informed Consent Forms, signed by the IRB chairperson or designee; copy of the Informed Consent Forms that were reviewed and approved by the IRB.

### 18.2 Study Site Training

Before initiation of the study, the Sponsor-Investigator, or its designated representatives will review and discuss the following items with the Investigator and clinic staff: the protocol, study procedures, record keeping and administrative requirements, drug accountability, AE reporting, Good Clinical Practice guidelines, monitoring requirements, and the ability of the site to satisfactorily complete the protocol.

### 18.3 Documentation

The PI and study staff has responsibility for maintaining a comprehensive and centralized filing system containing all study-related documentation. These files must be suitable for inspection by the Sponsor, the FDA, and/or other applicable regulatory agencies/competent authorities at any time, and should consist of the following elements: subject files (complete medical records, laboratory data, supporting source documentation, and the Informed Consent); study files (the protocol with all amendments, copies of all pre-study documentation, and all correspondence between the Competent Authorities, IRB/EC, site, and Sponsor); and drug accountability files, containing a complete account of the receipt and disposition of the study drug.

### 18.4 Data Collection

Case report forms must be completed and submitted for each subject enrolled in the study. Any changes or corrections made to the CRF/eCRF must be subsequently reviewed and signed by the PI. All data fields in the CRF/eCRF must be completed to avoid queries.

### 18.5 Protocol Interpretation and Compliance

The procedures defined in the protocol are carefully reviewed by the PI and his/her staff prior to the time of study initiation to ensure accurate representation and implementation. Protocol amendments, if any, are reviewed and implemented promptly following IRB/EC and relevant Competent Authorities approval. The Sponsor is responsible for submitting protocol amendments to the FDA as described in 21 CFR § 312.30 (Protocol Amendments) and other regulatory agencies according to national, state or local requirements. The Sponsor, or its designee, is always available to answer protocol- or subject-related questions.

### 18.6 Study Monitoring and Data Collection

Institutional support of trial monitoring will be in accordance with the FHCRC/University of Washington Cancer Consortium Institutional Data and Safety Monitoring Plan. Under the provisions of this plan, FHCRC Clinical Research Support coordinates data and compliance monitoring conducted by consultants, contract research organizations, or FHCRC employees unaffiliated with the conduct of the

study. Independent monitoring visits occur at specified intervals determined by the assessed risk level of the study and the findings of previous visits per the institutional DSMP.

In addition, protocols are reviewed at least annually and as needed by the Consortium Data and Safety Monitoring Committee (DSMC), FHCRC Scientific Review Committee (SRC) and the FHCRC/University of Washington Cancer Consortium Institutional Review Board (IRB). The review committees evaluate accrual, adverse events, stopping rules, and adherence to the applicable data and safety monitoring plan for studies actively enrolling or treating subjects. The IRB reviews the study progress and safety information to assess continued acceptability of the risk-benefit ratio for human subjects. Approval of committees as applicable is necessary to continue the study.

The trial will comply with the standard guidelines set forth by these regulatory committees and other institutional, state and federal guidelines.

### **18.7 Disclosure of Data/Publication**

Individual subject medical information obtained as a result of this study is considered confidential and disclosure to third parties other than those noted below is prohibited. Such medical information may be given to the subject's personal physician or to other appropriate medical personnel responsible for the subject's welfare. Data generated as a result of this study are to be available for inspection on request by the FDA or other regulatory agencies, the Sponsor or its designee and by the IRB/EC.

It is anticipated that the final results of this study will be submitted to a peer-reviewed scientific journal. Authorship on such a paper will be acknowledged with customary scientific practice. As such, without the expressed permission of the Sponsor, only clinical Study data relating the Study as a whole will be published.

### **18.8 Ethical Considerations**

The Investigator agrees to conduct this study in accordance with applicable United States FDA clinical trial regulations and guidelines, applicable United States FDA clinical trial regulations and guidelines, the ICH (E6) GCP guidelines, the IRB/EC and local legal requirements and with the Declaration of Helsinki (1989). The Investigator will conduct all aspects of this study in accordance with all national, state, and local laws of the applicable regulatory agencies.

### **18.9 Informed Consent**

The PI or qualified designee assumes the responsibility of obtaining written Informed Consent for each subject or the subject's legally authorized representative before any study-specific procedures are performed.

Subjects meeting the criteria set forth in the protocol will be offered the opportunity to participate in the study. To avoid introduction of bias, the Investigator must exercise no selectivity with regard to offering eligible subjects the opportunity to participate in the study. Subjects or parents/legal guardians of all candidate subjects will receive a comprehensive explanation of the proposed treatment, including the nature of the therapy, alternative therapies available, any known previously experienced adverse reactions, the investigational status of the study drug, and other factors that are part of obtaining a proper Informed Consent. Subjects will be given the opportunity to ask questions concerning the study, and adequate time to consider their decision to or not to participate.

Informed Consent will be documented by the use of a written Consent Form that includes all the elements required by FDA regulations and ICH guidelines. The Sponsor or designee will review the

informed consent prior to submission to the IRB/EC. The form is to be signed and dated by the subject or subject's legally authorized representative and by the person who administers the consent process. A copy of the signed form will be given to the person who signed it, the original signed Consent Form will be filed with the subject's medical records, and copy maintained with the subject's study records. The date and time of time of the Informed Consent must be recorded in the source documents.

If an amendment to the protocol changes the subject participation schedule in scope or activity, or increases the potential risk to the subject, the Informed Consent Form must be amended. Any amended Informed Consent must be reviewed by the Sponsor or designee and approved by the IRB/EC prior to use. The revised Informed Consent Form must be used to obtain re-consent from any subjects currently enrolled in the study if the subject is affected by the amendment and must be used to document consent from any new subjects enrolled after the approval date of the amendment.

### **18.10 Institutional Review Board/Ethics Committee**

The PI will assure that an appropriately constituted IRB/EC that complies with the requirements of 21 CFR Section 56 or written assurance of compliance with ICH (E6) guidelines will be responsible for the initial and continuing review and approval of the clinical study. Before initiation of the study, the PI or designee will forward copies of the protocol and Consent Form to be used for the study to the IRB/EC for its review and approval. A photocopy of the IRB/EC notification of approval must be forwarded to the Sponsor or its designee before any investigational supplies will be shipped to the PI.

The PI or designee will also assure that all changes in the research activity and all unanticipated problems involving risks to human subjects or others will be reported promptly to the IRB/EC, and that no changes will be made to the protocol without prior Sponsor and IRB/EC approval, except where necessary to eliminate apparent immediate hazards to human subjects.

Copies of all study-related correspondence between the Investigator and the IRB/EC must be provided to the Sponsor, or its designee, by the Investigator. The PI or designee must promptly notify the IRB/EC of any SAE occurring at the site and of any safety reports (e.g., IND Safety Reports) received from the Sponsor, or its designee, and must copy the Sponsor, or its designee on that correspondence.

The Investigator or designee will be responsible for submitting periodic progress reports to the IRB/EC at intervals appropriate to the degree of subject risk involved in the study, but not less than once per year and at the completion or termination of the study.

### **18.11 Subject Privacy**

The Sponsor-Investigator affirm and uphold the principle of the subject's right to privacy. The Sponsor-Investigator and its designees and the Investigator shall comply with applicable national and local privacy laws.

## 19.0 APPENDICES

Appendix A: Study Calendar

Appendix B: ECOG Performance Status Scale

Appendix C: Lugano Criteria

Appendix D: IWCLL Criteria

Appendix E: IMWG Criteria

## 19.1 Appendix A: Study Calendar

| Required Studies  | Screening Period | Cycle 1 Day 1 | Cycle 1 Day 8 | Cycle 1 Day 15 | Cycle 1 Day 22 | Cycle 2 Day 1 | C2D22  | Cycles 3-6 Day 1 | Cycle 7 + Day 1 | Post Therapy | Long-term Follow-up  |
|---|------------------|---------------|---------------|----------------|----------------|---------------|--------|------------------|-----------------|--------------|----------------------------------|
| Scheduling and Timing   | -28 to -1d       | +/- 3d        | +/- 3d        | +/- 3d         | +/- 3d         | +/- 3d        | +/- 3d | +/- 3d           | +/- 3d          | +/- 14 days  |                                  |
| Informed consent  | X                |               |               |                |                |               |        |                  |                 |              |                                  |
| Inclusion/Exclusion criteria  |                  |               |               |                |                |               |        |                  |                 |              |                                  |
| AE Assessment   | X                | X             |               |                |                | X             |        | X                | X               | X            |                                  |
| Medical history   | X                |               |               |                |                |               |        |                  |                 |              |                                  |
| Medication review (prior and concomitant)   | X                | X             |               |                |                | X             |        | X                | X               | X            |                                  |
| Trial treatment administration  |                  | X             |               |                |                | X             |        | X                | X               |              |                                  |
| Post-study anticancer therapy status  |                  |               |               |                |                |               |        |                  |                 | X            |                                  |
| Survival status   |                  |               |               |                |                |               |        |                  |                 |              | X                                |
| Vital signs   | X                | X             |               |                |                | X             |        | X                | X               | X            |                                  |
| Physical exam   | X                | X             |               |                |                | X             |        | X                | X               | X            |                                  |
| ECOG performance status   | X                | X             |               |                |                | X             |        | X                | X               | X            |                                  |
| Labs   |                  |               |               |                |                |               |        |                  |                 |              |                                  |
| CBC and differential  | X                | X             | X             | X              | X              | X             | X      | X                | X               | X            |                                  |
| Comprehensive metabolic panel including LDH, Mg, Phosphate, and direct bilirubin  | X                | X             | X             | X              | X              | X             | X      | X                | X               | X            |                                  |
| CRP   | X                | X             |               |                |                | X             | X      |                  |                 |              |                                  |
| Ferritin  | X                | X             | X             | X              | X              | X             | X      |                  |                 |              |                                  |
| Uric acid   | X                | X             | X             | X              | X              | X             | X      |                  |                 |              |                                  |
| Coagulation panel   | X                | X             | X             | X              | X              | X             | X      |                  |                 |              |                                  |
| Serum free light chain    | X                | X             |               |                |                |               |        |                  |                 |              |                                  |
| SPEP    | X                |               |               |                |                |               |        |                  |                 |              |                                  |
| Urinalysis  | X                |               |               |                |                |               |        |                  |                 |              |                                  |
| T3, FT4, and TSH  | X                | X             |               |                |                |               |        |                  |                 |              |                                  |
| Bone marrow studies   | X                |               |               |                |                |               |        |                  |                 |              |                                  |
| Pregnancy test    | X                |               |               |                |                |               |        |                  |                 |              |                                  |
| Tumor assessment    | X                |               |               |                |                |               |        | X                | X               | X            |                                  |
| Correlative studies blood draw    | X                | X             | X             | X              | X              | X             | X      | X                | X               | X            |                                  |
| Cytokine Panel  | X                | X             | X             | X              | X              | X             | X      | X                | X               | X            |                                  |
| Pre-Treatment Archival Tumor Biopsy   | X                |               |               |                |                |               |        |                  |                 |              |                                  |

Adverse events will be recorded from the time of a subject signing consent up until 30 days after the last dose of nivolumab, or 90 days after the last dose of nivolumab in the case of serious adverse events.

For subjects with multiple myeloma only.

The Sponsor-Investigator or sub-Investigator may waive screening bone marrow aspirate and biopsy requirements. For subjects with CLL/SLL and MM, repeat bone marrow biopsy only to be done after screening to confirm CR

Pregnancy test is only required in women of childbearing potential. Verbal report of pregnancy will be reported during conduct of the trial.

Tumor assessment imaging (see section 11.1.2.5) will be performed prior to cycle 3 (within 7 days of scheduled treatment dose) and every 3 cycles thereafter. Tumor assessment labs and/or imaging will also be performed as indicated per clinical standard of care (e.g. as appropriate for disease, to evaluate clinical suspicion of disease progression). Screening PET-CT and diagnostic CT done prior to screening up to day -42 may

be used for screening assessment. PET-CT and diagnostic CT will be performed at screening, then after 2 cycles on cycle 2 day 22. Thereafter, tumor assessment will comprise diagnostic CT of chest, abdomen, pelvis every 3 months. For multiple myeloma only, PET-CT should only be done amongst subjects in whom the only measurable disease is by imaging criteria – both at screening and for follow-up.

End of treatment evaluations should be done within 30 days (+/- 14 days) of the last dose of nivolumab or prior to the start of a new anti-cancer drug, whichever is first.

Correlative studies to include peripheral blood for storage for future biomarker analyses. Please see section 15 for details on blood collection and storage.

Long-term follow-up should be done according to the subject's physician standard of care. This may be performed at subjects' local physician's offices. Long-term follow-up will assess survival and disease progression. Subjects may be contacted by the study team until death, subject withdrawal of consent, lost to follow-up, or study termination, whichever occurs first.

If available, will be tested for PD-1 and PD-L1 IHC

The use of growth factors or transfusions to meet hematologic eligibility criteria is allowed

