### 9.4 Study Response Assessments

Safety assessment will occur through the study and consist of continuous surveillance and recording of adverse events (AEs) and serious adverse events (SAEs).

After the end of treatment, each subject will be followed for 30 days for adverse event monitoring (serious adverse events may be collected for 90 days after the end of treatment). Subjects may have post-treatment follow-up for disease status up to 5 years, or until disease progression, initiating a non-study cancer treatment, withdrawing consent, or becoming lost to follow-up.

4. Non-Hodgkin Lymphoma: PET-CT and CT (Diagnostic quality) after 2 cycles (8 weeks), then Diagnostic CT of chest, abdomen, and pelvis every 3 cycles (12 weeks) thereafter. Response assessment will be based on the Lugano Criteria
  - a. Initial response assessment after 2 cycles (8 weeks) with PET-CT and diagnostic CT
  - b. Diagnostic CT every 3 cycles thereafter
5. Chronic lymphocytic leukemia: PET-CT and CT (Diagnostic quality) after 2 cycles (8 weeks), then Diagnostic CT every 3 cycles (12 weeks) thereafter. A bone marrow aspirate +/- biopsy will be obtained at screening and to confirm CR. Response assessment based on IWCLL criteria
  - a. Initial response assessment after 2 cycles (8 weeks) with PET-CT and diagnostic CT
  - b. Diagnostic CT every 3 cycles (12 weeks) thereafter
6. Multiple myeloma: Assessment of serum protein electrophoresis (SPEP), serum free light chains (sFLC), every 4 weeks. 24-hour urine assessment of Bence-Jones Proteinuria only in subject who have this as sole marker of disease. Response assessment based on the IMWG. A bone marrow aspirate and biopsy will be obtained at screening and to confirm CR. PET-CT only to be performed for subjects with plasmacytoma as the only site of measurable disease at screening, after 2 cycles, then every 3 cycles (12 weeks) thereafter.

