## 9.5 Nivolumab – Dosing Delays and Modifications

Adverse events (both non-serious and serious) associated with nivolumab exposure may represent an immunologic etiology. These adverse events may occur shortly after the first dose or several months after the last dose of treatment. The dose of nivolumab must be withheld for drug-related toxicities and severe or life-threatening AEs as per Table 5 below:

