## 9.6 Subject Withdrawal/Discontinuation Criteria

Subjects may withdraw consent at any time for any reason or be dropped from the trial at the discretion of the investigator should any untoward effect occur. In addition, a subject may be withdrawn by the investigator for significant subject noncompliance with protocol requirements, or for administrative and/or other safety reasons. Subjects who require cessation of study therapy but do not withdraw consent may remain in standard follow-up for up to 5 years.

A subject must be discontinued from the trial for any of the following reasons:

- The subject or legal representative (such as a parent or legal guardian) withdraws consent.
- Confirmed radiographic disease progression
- Unacceptable adverse experiences
- Intercurrent illness that prevents further administration of treatment
- Investigator's decision to withdraw the subject
- The subject has a confirmed positive serum pregnancy test
- Noncompliance with trial treatment or procedure requirements
- The subject is lost to follow-up
- Administrative reasons

The End of Treatment and Follow-up visit procedures are listed in Appendix A (Study Calendar) and Section 11.1.5 (Visit Requirements). After the end of treatment, each subject will be followed for 30 days for adverse event and 90 days for serious adverse event monitoring. Subjects may have post-treatment follow-up up to 5 years per routine standard of care for survival and disease status.

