## 11.1.2 Clinical Procedures/Assessments

### 11.1.2.1 Adverse Event (AE) Monitoring

Each subject will be assessed to evaluate for potential new or worsening AEs as specified in the Study Calendar and more frequently if clinically indicated. Adverse experiences will be graded and recorded throughout the study and for 30 days after the last dose of study drug according to NCI CTCAE Version 5.0. Toxicities will be characterized in terms regarding seriousness, causality, toxicity grading, expectedness, and action taken with regard to trial treatment.

For subjects receiving treatment with nivolumab all AEs of unknown etiology associated with nivolumab exposure should be evaluated to determine if it is possibly an event of clinical interest (ECI) of a potentially immunologic etiology (termed immune-related adverse events, or irAEs).

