#### 11.1.5.3 End-of-treatment Visit

EOT Visits for all subjects who discontinue from the study should occur at least 7 days, but  $\leq$  30 days, after the last dose of IP and prior to beginning other treatment (+/- 14 days).

The off-study visit will include laboratory studies, medical history, physical exam, remission status, concomitant medications, adverse events, and documentation of any ECI and subsequent management, as in the Study Calendar. All AEs that occur prior to the end-of-treatment visit should be recorded. Subjects with an AE of Grade > 1 will be followed for 30 days. SAEs that occur within 90 days of the end of treatment should also be followed and recorded.

After the end-of-study visit, additional follow-up will be conducted as per routine standard of care for up to 5 years unless other criteria for withdrawal are met. Long-term follow-up may be performed at subjects' local physician's offices. Long-term follow-up will assess survival and disease progression; for clarification, subjects may be contacted by the study team until death, subject withdrawal of consent, lost to follow-up, or study termination, whichever occurs first.

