## 13.0 ADVERSE EVENTS

### 13.1 Adverse Event

According to ICH guidelines (Federal Register, 1997; 62(90):25691-25709) and 21 CFR 312.32, IND Safety Reports, and ICH E2A, *Definitions and Standards for Expedited Reporting*, an adverse event is defined as follows:

*An adverse event is any untoward medical occurrence in a clinical investigation subject administered a medicinal product and which does not necessarily have a causal relationship with this treatment. An AE can therefore be any unfavorable and unintended sign (including an abnormal laboratory finding), symptom, or disease temporally associated with the use of a medicinal product, whether or not considered related to the medicinal product.*

*Abnormal laboratory values for laboratory parameters specified in the study should not be recorded as an adverse event unless an intervention is required (repeat testing to confirm the abnormality is not considered intervention), the laboratory abnormality results in a serious adverse event or the adverse event results in study termination or interruption/discontinuation of study treatment.*

Adverse events and Serious Adverse Events are collected from the time of screening until day 30 (AEs), and day 90 (SAEs).

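### New non-serious immune-related or Grade 3 drug-related events starting more than 30 days after treatment have no route into the safety data, although section 9.5 expects late onset

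*Combined protocol and SAP*

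**What the plan says.** **Non-serious events.** Appendix A, footnote 1: "Adverse events will be recorded from the time of a subject signing consent up until 30 days after the last dose of nivolumab". Section 11.1.2.1 says that events are "graded and recorded throughout the study and for 30 days after the last dose of study drug". Section 9.6 says that after treatment "each subject will be followed for 30 days for adverse event and 90 days for serious adverse event monitoring". The synopsis and 9.4 also give 30 days, counted from the end of treatment. Section 13.1 says that events "are collected from the time of screening until day 30 (AEs), and day 90 (SAEs"), without saying from what date the days are counted.

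**Serious events.** The sentence in footnote 1 goes on: "or 90 days after the last dose of nivolumab in the case of serious adverse events". Section 11.1.5.3 says "SAEs that occur within 90 days of the end of treatment should also be followed and recorded". Only the synopsis and 9.4 are permissive: "serious adverse events may be collected for 90 days after the end of treatment".

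**Late onset.** Section 9.5, speaking of serious and non-serious events alike, says: "These adverse events may occur shortly after the first dose or several months after the last dose of treatment".

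**After the window.** Section 11.1.5.3 and Appendix A, footnote 7 limit long-term follow-up to survival and disease progression, under the subject's standard of care.

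**Stopping rule (6.1 and 16.4).** The rule is defined on the rate of discontinuation due to medically significant, attributable Grade 3 or greater events. Its operational form counts subjects with unacceptable toxicity or attributable Grade 3 or greater events. Neither form states an observation window.

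**The concern.** The protocol describes a risk that can appear months after dosing, then stops recording non-serious events about one dosing cycle after the last dose. Section 13.7.1 asks that non-serious events be followed to resolution or stabilization, but that concerns events already recorded and does not bring in new ones.

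Adverse events are a secondary endpoint (5.3), and 16.2 lists safety among the primary objectives. The setting is new: a checkpoint inhibitor given after CAR T cells, where the late safety profile is part of what the trial should describe. With 20 subjects, a few unrecorded events visibly change the reported rate. The operational stopping rule also turns on single events, for example 5 against 6 of 20.

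**Working it through.** **1. Length of the window.** The cycle is 28 days (9.1) and the window 30 days, so 30 − 28 = 2 days. With the ±3-day dosing window, the next dose could fall 28 + 3 = 31 days after the last one, which is after the window has closed.

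**2. Sections side by side.**

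| Section | Non-serious | Serious | Counted from |
|---|---|---|---|
| Synopsis; 9.4 | 30 days | 90 days, *may* | end of treatment |
| 9.6 | 30 days | 90 days, *will* | end of treatment |
| 11.1.2.1 | 30 days | not separated | last dose |
| 11.1.5.3 | events before the end-of-treatment visit | 90 days, *should* | visit; end of treatment |
| 13.1 | day 30 | day 90, *are collected* | not stated |
| Appendix A, footnote 1 | 30 days | 90 days, *will* | last dose |

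The end-of-treatment visit falls at least 7 and at most 30 days after the last dose, with ±14 days. On that section's wording, collection could close as early as day 7 or as late as day 30 + 14 = 44.

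**3. What the anchor changes.** Take a subject who progresses at the assessment after 2 cycles, with doses on days 1 and 29. From the last dose, the window closes on day 29 + 30 = 59, only 3 days after cycle 2 ends on day 56. If end of treatment is read as day 56, it closes on day 56 + 30 = 86. The difference is 27 days.

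**4. Drug remaining.** Section 4.8.1.3 gives about 25 days as the upper limit of the half-life. The fraction remaining is 0.5^(days/25):
- day 30: 0.5^1.2 = 0.435, about 44%
- day 90: 0.5^3.6 = 0.082, about 8%

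These are upper-end exposure figures, not event rates.

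**5. Stopping rule: the plan's own figures.** The boundaries are 2 of ≤6, 3 of ≤9, 4 of ≤13, 5 of ≤16 and 6 of ≤20. Let P(n,k) be the probability of k events in n subjects without a trigger so far. Then P(n,k) = P(n−1,k)(1−p) + P(n−1,k−1)p, and paths that reach the boundary are removed and added to the suspension probability.
- p = 2.5%: 0.0091, against the stated 0.01. This agrees.
- p = 40%: 0.942, against the stated 0.91. This does not agree to within 2 points. Without the 6-of-20 look it is 0.918. The discrepancy is a separate matter; the rule as written is used below.

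**6. Sensitivity to unrecorded events.** The documents give no late-onset rate, so the share f of countable events never recorded is an assumption. The rate the rule sees is p(1−f).

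| f | p = 40%: seen | suspension | p = 30%: seen | suspension |
|---|---|---|---|---|
| 0 | 0.40 | 0.94 | 0.30 | 0.78 |
| 10% | 0.36 | 0.89 | 0.27 | 0.69 |
| 20% | 0.32 | 0.82 | 0.24 | 0.60 |
| 30% | 0.28 | 0.72 | 0.21 | 0.50 |
| 50% | 0.20 | 0.46 | 0.15 | 0.28 |

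The table applies only to the operational count. Under the formal definition, an event that starts after treatment has ended cannot cause a discontinuation, so the window has no effect.

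**The case against.** **SAE collection is not optional.** A reader of 9.4 alone might infer that serious events after treatment are collected only at discretion. The documents do not support this. Sections 9.6, 11.1.5.3, 13.1 and the second half of the footnote 1 sentence all set 90 days in firmer terms. What remains is a wording conflict.

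**Late Grade 3 events are not lost in general.** Medically significant is itself an SAE criterion (13.2), and 13.7.1 asks for an SAE form whenever seriousness is in doubt. Many important late immune events should therefore be captured to day 90. The gap concerns events judged non-serious.

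**Laboratory findings are governed by another rule.** Under 13.1, an abnormal value is not an adverse event unless it needs intervention, leads to a serious event, or interrupts or ends treatment. An untreated, non-serious value found after treatment would go unrecorded whatever the window. This narrows the gap but leaves clinical events, and values that need treatment without being serious.

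**The remedy is partial.** Ninety days may not cover the late onset that 9.5 describes. The calendar schedules no day-90 visit or laboratory tests, and attribution is harder once another therapy has started. All of this stands. It limits what an extension can achieve but does not justify dropping known attributable events while subjects are already being monitored for SAEs (9.6).

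**Conclusion.** The concern holds in a limited form. New non-serious drug-related Grade 3 or immune-related events after about day 30 have no route into the safety endpoint, which conflicts with the protocol's own description of late onset. The loss to the endpoint does not depend on how the stopping rule is read.

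For the stopping rule, a reader might infer that late events are being withheld from it altogether. The documents support less: only the operational count can be understated, and only by non-serious attributable Grade 3 or greater events after the window and serious ones after day 90.

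The number of events lost cannot be derived from the documents. The suspension probabilities rest on an assumed missing share, applied equally to all subjects, and show sensitivity rather than an expected loss. This is an inexpensive improvement to data capture, not a flaw that undermines the design.

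**What to change.** 1. In the synopsis, 9.4, 9.6, 11.1.2.1, 13.1 and Appendix A footnote 1, record investigator-assessed immune-related events and drug-attributable Grade 3 or greater events, serious or not, to 90 days after the last dose. Use the follow-up already required for SAEs, add no tests, and include these events in the safety summaries of 16.1. Align 11.1.5.3 with this.
2. Reconcile the permissive SAE wording in the synopsis and 9.4 with the firm 90-day wording elsewhere.
3. Use one anchor throughout. Last dose, as in footnote 1, is a recorded date that needs no interpretation.
4. Reconcile the two definitions of the stopping rule in 6.1 and 16.4, and state whether events starting after treatment count and over what period.
5. Record the start date of any new anticancer therapy beside each late event, so that attribution can be judged. Section 11.1.1.5.2 already collects this therapy.

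The cost is wording and a few more records in 20 subjects. The downsides are slightly more data collection and less certain attribution after a change of therapy. Without added testing, silent laboratory abnormalities would still go undetected.
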